### 3.8 Contingency Reinforcement for Smoking Cessation (for healthy smokers)

We plan to image smokers during the first 8 weeks of abstinence. Contingency management techniques have been successfully used to help smokers quit smoking by a number of investigators including our group for many years (34-36).

We will help the subjects set a quit date and prior to the quit date they will meet with the research staff who will provide them with brief advice on quitting smoking based on AHCPR guidelines (The Smoking Cessation and Clinical Practice Guideline Panel and Staff, 1996). They will be advised about the risks and benefits of quitting smoking and told that they will be monitored daily to ensure abstinence. Subjects will be informed of payment schedules (see below) for CO levels indicating abstinence and also given information on how quit rates in the first week of smoking cessation predicted sustained abstinence. We use CO levels < 11 ppm to define abstinence from cigarettes. During the first week of abstinence we will obtain CO levels during contingency management meetings from subjects up to twice daily. In addition, we will obtain urine samples once daily to measure cotinine levels (a nicotine metabolite). These meeting will occur either in the research office, the Yale PET center, or in a midway point if subjects travel a far distance.

For each contingency management appointment, subjects will get \$10 if their CO levels are less than 1 ppm and urine cotinine levels are less than 100 ng/ml.

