### **3.8a Contingency Reinforcement for Smoking Cessation (healthy controls)**

We plan to image smokers whom have been abstinent from smoking for approximately 1 week (with and without schizophrenia), 2 weeks (controls only) and 6 weeks (controls only). Contingency management techniques have been successfully used to reduce CO levels in non-treatment seeking smokers by a number of investigators (158-160).

Subjects will set a quit date and prior to the quit date they meet with the research staff who will provide them with brief advice on quitting smoking based on AHCPR guidelines (The Smoking Cessation and Clinical Practice Guideline Panel and Staff, 1996). They will be advised about the risks and benefits of quitting smoking and told that they will be monitored daily to ensure abstinence. Subjects will be informed of payment schedules (see below) for CO levels indicating abstinence and also given information on how quit rates in the first week of smoking cessation predicted sustained abstinence. We use CO levels < 11 ppm to define abstinence from cigarettes. During the first week of abstinence we will obtain CO levels from subjects up to twice daily. In addition, we will obtain urine samples once daily to measure cotinine levels (a nicotine metabolite).

For each contingency management appointment, subjects will get \$10 if their CO levels are less than 11 ppm and urine cotinine levels are less than 100 ng/ml.

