**Aim 1. To determine amphetamine-induced DA release in nonsmokers and in tobacco smokers during acute and prolonged withdrawal.** We will scan 50 Healthy Smokers and 50

Non Smoker healthy controls. Each tobacco smoking subject will participate in up to 4 [C]PHNO PET scans, one pair of scans during the first 2 weeks of smoking abstinence and, for those who remain abstinent, the option to have another pair of scans at 2-8 weeks abstinence. We aim to have at least one week in between sets of scans. Ideally, two PET scans will be carried out in the same day. We first obtain a baseline scan, then approximately three hours before the second scan, amphetamine (0.5 mg/kg, PO) will be administered. Nonsmokers will only be asked to participate in one set of scans. We hypothesize that smokers at 1-2 weeks of withdrawal will have amphetamine-induced DA release that is blunted compared to healthy nonsmokers. We also hypothesize that the smokers who are scanned again at 2-8 weeks withdrawal will exhibit some ‘normalization’ of the dopamine system and will have a larger amphetamine-induced DA release compared to their first scan. We hypothesize that smokers with amphetamine-induced DA release similar to nonsmokers, or that increases over time, will have better abstinence outcomes.

2. **Background:** Describe the background information that led to the plan for this project. Provide references to support the expectation of obtaining useful scientific data.

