## **PET**

PET scans may be performed on the High Resolution Research Tomograph (HRRT, 2-3 mm resolution) or another similar camera. Venous catheters will be used for i.v. administration of the radiotracers, venous blood sampling of activity, and for venous blood sampling of amphetamine plasma levels and hormone levels. At the beginning of scan, the subject's head will be immobilized and a transmission scan will be obtained for attenuation correction. PET scans will be acquired using bolus or bolus to infusion administration of up to 10 mCi of [C]PHNO and subjects will be scanned for up to 2 hours. Dynamic images of radioactivity concentration are reconstructed with corrections for attenuation, normalization, random events, scatter, and deadtime. Subject motion is corrected automatically on an event-by-event basis with the Vicra motion tracking system. Vital signs (blood pressure, pulse and respiration) are collected prior to and during each PET scan. Urine pregnancy test will be again administered on the PET scan day prior to the initiation of any imaging procedures. Smoking abstinence, when appropriate, will also be confirmed for smoking subjects prior to PET scanning.

PET scanning will then proceed as following for each aim:

Aim 1. Smoking subjects will be asked to come in for two [C]PHNO scans with amphetamine administration. The first scan will be during the first 2 weeks of withdrawal with the option to come back again at 2-8 weeks of withdrawal. Nonsmoking subjects will be asked to come in for one set of two [C]PHNO scans with amphetamine administration. Up to 10 mCi of PHNO will be administered per scan. After the first scan, subjects will take amphetamine (0.5mg/kg) by mouth, and then will be imaged again with PHNO. If technical difficulties arise, the second PET scan of the set may have to be re-scheduled and will be scheduled as soon as possible. In that case, subjects may be asked to re-take amphetamine on the day of the rescheduled PHNO scan, approximately 3 hrs prior to the scan. Amphetamine dose will not exceed 50mg per scan. Subjects will not be allowed to drive home.

In the rare event that a scan would fail post injection, subjects may repeat each scan set up to a total of 8 PHNO scans for smokers and 4 PHNO scans for nonsmokers.

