## SECTION VII: RESEARCH ALTERNATIVES AND ECONOMIC CONSIDERATIONS

1. **Alternatives:** What alternatives are available to the study subjects outside of the research?

The alternative to participation in this research protocol is to not participate. Subjects will be informed that they are free to choose not to participate and, if they do agree to become a subject, they will be free to withdraw from the study at any time during its course. They will also be informed that if they choose not to participate or if they withdraw, it will not adversely affect their relationship with their doctors or the hospital (see attached Consent Form).

2. **Payments for Participation (Economic Considerations):** Describe any payments that will be made to subjects and the conditions for receiving this compensation.

The subjects will be compensated for their time commitment and inconveniences necessary for completing the study. Subjects will have no financial responsibilities for any portion of the study. For Aim 1 payment would be \$350 for each PHNO PET scan, \$50 for each MRI scan, and \$40 for cognitive testing at baseline. Subjects who participate in the Probabilistic Reward Task may also be compensated for the amount that they “win” during the task, up to \$50. Subjects may also receive an extra \$10 for each Cold Pressor Task that they participate in. Subjects will be paid either by check, and are advised to allow 4-6 weeks for receipt of payment, or they will be given a credit card or cash. In addition, subjects will be provided with a light meal, at the end of the PET imaging day. Reasonable transportation costs will be reimbursed. Receipts must be submitted. If participation in the PET Scan has already begun, then compensation will be based on involvement in the study, and will be up to the discretion of the PI. Smokers will also receive \$10 for each contingency management appointment at which their carbon monoxide and urine cotinine levels show that they have not smoked. Subjects can decide if they want to receive this amount at each appointment in cash, or receive it all at the end of the study in the form of a credit card or check or cash. Smokers will receive an additional \$100 bonus for completing the study.

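### PHNO protocol, section 3.8: abstinence is defined as CO below 11 ppm, but the abstinence payment requires CO below 1 ppm

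*Combined protocol and SAP*

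**What the plan says.** The combined document holds two protocols, one for the NCFHEB studies and one for the PHNO amphetamine study. The point concerns section 3.8 of the PHNO protocol, which makes three statements in sequence:

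- On what the payments are for: "Subjects will be informed of payment schedules (see below) for CO levels indicating abstinence".
- On the definition: "We use CO levels < 11 ppm to define abstinence from cigarettes".
- On the payment itself, $10 is given at each contingency management appointment if "their CO levels are less than 1 ppm and urine cotinine levels are less than 100 ng/ml".

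The payments part of Section VII of the same protocol gives $10 "for each contingency management appointment at which their carbon monoxide and urine cotinine levels show that they have not smoked", with no ppm figure.

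Section 3.8a of the NCFHEB protocol, the parallel text for healthy smokers, has the same 11 ppm definition and pays $10 if "their CO levels are less than 11 ppm and urine cotinine levels are less than 100 ng/ml".

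**The concern.** The pointer forward to the payment schedule ties the payment sentence to the abstinence definition, so the two CO figures should agree. They do not, and no reason is given for a stricter payment rule.

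The payment sentence holds the only numeric rule in the PHNO protocol for releasing the abstinence reward, and contingency management is the technique the study relies on to help smokers quit. Staff who follow section 3.8 literally would refuse payment to people the protocol calls abstinent. Staff who follow Section VII, read with the 11 ppm definition, would pay them, subject to cotinine. The same reading could therefore be handled in two ways.

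Abstinence also matters to the design. The first scan pair is set at about 1 to 2 weeks after quitting, and Aim 1 offers, "for those who remain abstinent, the option to have another pair of scans at 2-8 weeks abstinence". The reward is one of the means of keeping smokers available for those scans.

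**Working it through.** No power, sample size or alpha figure is involved, so the check sets the texts side by side and counts the CO values on which they disagree.

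**Inputs**

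- Abstinence definition, PHNO section 3.8: CO < 11 ppm.
- Payment rule, PHNO section 3.8: CO < 1 ppm and urine cotinine < 100 ng/ml.
- Payment rule, PHNO Section VII: CO and cotinine show no smoking; no number.
- Definition and payment rule, NCFHEB section 3.8a: CO < 11 ppm in both; the payment also needs urine cotinine < 100 ng/ml.

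**Step 1. Where the definition and the payment rule disagree.** Abstinent on CO means CO < 11. The CO part of the payment rule is met at CO < 1. Readings that are abstinent but cannot be paid are therefore those with 1 ≤ CO < 11 ppm. The cut-offs differ by 11 − 1 = 10 ppm.

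**Step 2. Whether cotinine removes the conflict.** The two payment conditions are joined by 'and'. If CO is 1 ppm or more, the CO condition fails and no cotinine value can release the payment. Cotinine does not resolve the conflict.

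**Step 3. Size, in whole ppm.**

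| | CO values | Count |
|---|---|---|
| Abstinent by definition (CO < 11) | 0 to 10 | 11 |
| CO part of payment rule met (CO < 1) | 0 | 1 |
| Abstinent but cannot be paid | 1 to 10 | 11 − 1 = 10 |

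Share of abstinent values that cannot be paid: 10 / 11 = 90.9%, or 91%.

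**Step 4. The same count under the NCFHEB wording.** With CO < 11 in the payment rule, all 11 abstinent values pass the CO part: 11 − 11 = 0 excluded.

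**Step 5. Other CO cut-offs for smoking status.** The PHNO entry criterion for smokers (section 3.3) is CO > 8 ppm. The NCFHEB inpatient section (3.8b) uses CO < 10 ppm to confirm abstinence. The 1 ppm figure stands alone among these. A reading of 1 to 8 ppm would not meet the PHNO CO criterion for entry as a smoker, yet it earns no abstinence payment.

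**The case against.** The strongest reply is that this is a single lost digit with little consequence. The NCFHEB sentence matches in structure and cotinine limit and reads 11 ppm. The text was also read from PDF by a program, so a loss in extraction cannot be ruled out, although nothing marks a gap. Section VII of the PHNO protocol is where payment conditions belong; read with the 11 ppm definition it gives staff a workable rule, which makes literal use of 1 ppm less likely. That has weight, but Section VII states no number and so does not correct section 3.8.

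A second reply is that payment need not equal the definition. Even under the NCFHEB wording, a smoker with CO below 11 ppm and cotinine of 100 ng/ml or more meets the CO definition and goes unpaid. This is right: the conflict rests on section 3.8 describing the payments as being for CO levels that indicate abstinence, not on any general need for the two rules to match.

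Third, the effect on retention is not shown. The second scan pair depends on staying abstinent, not on having been paid. Section VII also provides $350 per PHNO scan ($700 for a pair) and a $100 completion bonus, neither tied to 1 ppm. This stands, and no effect on who is scanned is claimed. Nor does the 91% predict how often payment would be refused, since the documents give neither the CO meter's resolution nor a distribution of readings.

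None of these replies removes the contradiction within section 3.8.

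**Conclusion.** The concern holds. As written, section 3.8 of the PHNO protocol contradicts itself: it denies the abstinence reward at every CO value from 1 ppm to just under 11 ppm, all of which it defines as abstinent. That is 10 of the 11 whole-ppm values, on the assumption that CO is read in whole ppm.

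The number of smokers affected and any bias in the results cannot be derived from the documents. The power calculation and the analysis of the primary outcome do not use this figure. The consequence is confined to the incentive payments and to consistent handling of abstinence checks. A dropped digit is the likely explanation, but only the sponsor can confirm that. Because this is a threshold that staff apply at appointments, and the correction is nearly free, it should be corrected.

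**What to change.** Check the payment sentence in section 3.8 of the PHNO protocol against the source file, and have the sponsor confirm the intended CO cut-off. Then reconcile the two figures so that the CO part of the payment rule follows the stated definition. Suggested wording: $10 is paid if CO is below the abstinence cut-off stated above and urine cotinine is below 100 ng/ml. Section VII can then stand as it is.

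Optionally, the PET part of section 3.5, which says "Smoking abstinence, when appropriate, will also be confirmed for smoking subjects prior to PET scanning" without giving a criterion, could refer to the same definition. This is a convenience and not part of the conflict.

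The cost is one numeral or a cross-reference. No visit, measurement or analysis changes.

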#### 4. Genetic Testing N/A

**5. Subject Population** Provide a detailed description of the targeted population of human subjects for this research project.

Target numbers for participation are 40 Healthy controls and 50 Healthy Smokers. Healthy controls and healthy smokers will be recruited from the community through advertisements as approved by the Yale University Human Investigations Committee (HIC). Interested individuals contacting the clinic by phone in response to advertisements are told that the information they give over the phone is written down and discussed by the research team. They are advised that if they do not enroll in research with the clinic the information is destroyed, and that if they do, it becomes part of their research chart. A phone screen is completed after they give verbal authorization. If an individual appears to meet enrollment criteria and is interested in participating, a face-to-face interview is conducted. A release of information is obtained for review of any available historical and clinical data. Written authorization is also obtained from each subject, permitting the research team to use, create, or disclose the subject's PHI for research purposes. The nature of the project, procedures, relative risks and benefits, and alternatives to participation in the project are discussed with the individual. Following this discussion, the individual is given a copy of the consent form to review, and any questions are answered. We will obtain written consent from all participants.

**6. Subject Classifications:** Will subjects who may require additional safeguards or other considerations be enrolled in the study? If so, identify the population of subjects requiring special safeguards and provide a justification for their involvement.

a. Is this research proposal designed to enroll children who are wards of the state as potential subjects?  Yes  No (*If yes, see Instructions section VII #4 for further requirements*)

**7. Inclusion/Exclusion Criteria:** What are the criteria used to determine subject inclusion or exclusion?

**General inclusion criteria:**

- men and women, aged 18-55 years
- who are able to read and write
- who are able to give voluntary written informed consent
- have no current uncontrolled medical condition such as neurological, cardiovascular, endocrine, renal, liver, or thyroid pathology
- drink less than <21 drinks/week for women and less than <35 drinks per week for men
- If female, not pregnant or breast feeding
- If female of childbearing age, must use an acceptable method of birth control, as determined by the principal investigator
- do not suffer from claustrophobia or any MR contradictions
- willing to be followed up monthly after study participation via phone or email contact

**General exclusion criteria:**

- Presence of acute or unstable medical or neurological illness. Subjects will be excluded from the study if they present with any history of serious medical or neurological illness or if they show signs of a major medical or neurological illness on examination or lab testing including history of seizures, head injury, brain tumor, heart, liver or kidney disease, eating disorder, diabetes.
- Presence of an Axis I diagnosis other than nicotine dependence
- Regular use of any psychotropic drugs including anxiolytics and antidepressants and other over-the-counter medications and herbal products in the past six months other than THC, per the PI's discretion. The PI will take a number of factors into consideration on a case-by-case basis including type of psychotropic drug used, frequency, and dose.
- Pregnancy/Breast feeding
- Subjects with a pacemaker or other ferromagnetic material in body.
- Subjects with a sitting pulse rate >100 bpm will be excluded
- Subjects with hypertension defined as sitting systolic blood pressure of >160 mmHg and/or sitting diastolic blood pressure of >100 mmHg will be excluded. Those individuals with hypertension that is well controlled by medication (e.g., within the above mentioned range) are not excluded
- Specifically, we will exclude subjects who have any active clinically significant deviation from the normal range in their electrocardiogram (EKG). However, subjects who have abnormalities in their EKG but the condition has been present for a while and the study cardiologist has evaluated and feels comfortable with the condition, would not be excluded on the basis of their cardiac condition. Examples of conditions that may meet these criteria (e.g., condition has been present for a while) include but are not limited to T-wave abnormalities, atrial fibrillation, prolonged PR interval, and right bundle branch block.
- Subjects with history of prior radiation exposure for research purposes within the past year such that participation in this study would place them over FDA limits for annual radiation exposure. This guideline is an effective dose of 5 rem received per year.
- Subjects with current, past or anticipated exposure to radiation in the work place
- Blood donation within eight weeks of the start of the study.

- History of a bleeding disorder or are currently taking anticoagulants (such as Coumadin, Heparin, Pradaxa, Xarelto).

**8. How will eligibility be determined, and by whom?**

Eligibility to participate will be determined by the PI of this study after completion of the medical and psychiatric evaluation of the potential participant.

**9. Risks:** Describe the reasonably foreseeable risks, including risks to subject privacy, discomforts, or inconveniences associated with subjects' participation in the research.

Risks from this study include 1) risks associated with radiation exposure, 2) risks associated with MRI, 3) intravenous lines and blood drawing, 4) nicotine withdrawal symptoms, 5) amphetamine

**1. Risks Associated with Radiation**

The Yale New Haven Radiation Safety Committee and the FDA will review the use of radiation in this research study as the radiotracer [C]PHNO PET will be under IND # **134138**, This research study involves exposure to radiation from [C]PHNO PET scanning. This radiation exposure is not necessary for medical care and is for research purposes only.

For each individual [C]PHNO PET scan, subjects will receive up to ≤ 10 mCi of [C]PHNO, plus transmission scans. This is equal to an effective dose equivalent of 0.2146 rem per injection.

The maximum amount of radiation per year an individual subject will receive in this study is from up to 8 injections of ≤ 10mCi each of [C]PHNO, plus transmission scans. The intended amount is from up to 4 injections of ≤ 10mCi each of [C]PHNO for smokers and up to 2 injections of ≤ 10mCi each of [C]PHNO in nonsmokers, however in case of scan failures post injection we have included up to 8 injections if scan sets need to be repeated within the study time frame (i.e. 1-2 wks withdrawal and 2-8 wks withdrawal). Nonsmokers maximum number of injections including re-scans would be 4 scans total. Should the second scan of the set fail, we will make every effort to reschedule the scan for repeat within 1 wk, however if scheduling does not permit this, we may ask the subject to repeat the whole set due to timing related data.

Although each organ will receive a different dose, the maximum intended amount of radiation exposure subjects will receive per year from this study is equal to an effective dose equivalent of 0.858400001 rem for a total of up to 40 mCi of [C] PHNO in 4 injections of ≤ 10mCi each for smokers and 0.4292 rem for a total of up to 20 mCi [C] PHNO in 2 injections of ≤ 10mCi each for non smoker. This calculated value is used to relate the dose received by each organ to a single value.

However, if scans should need to be repeated the maximum dose for smokers would be equal to an effective dose of 1.716800002 rem from up to 8 injections and for non smokers would be 0.858400001 rem from up to 4 injections. We have every intention to limiting radiation exposure to subjects and avoiding re-scans if possible.

2 injections PHNO	0.4292 rem
-------------------	------------

4 injections PHNO	0.8584 rem
8 injections PHNO	1.7168 rem

The amount of radiation subjects will receive in this study is below the dose guidelines established by the FDA and monitored by the Yale University Radioactive Drug Research Committee for research subjects. This guideline sets an effective dose limit of 5 rem per year.

